
5 subjects, the muscles of interest were manually outlined on T2 maps at baseline, whereas 2M and 3M post-injections were mapped using software written in-house in IDL 8.1 (Exelis Inc, Boulder, CO). A histrogram of T2 relaxation times (ms) was constructed for the baseline scan for all voxels in the muscle. A Guassian function was used to calculate a mean and standard deviation for each muscle at baseline. We defined BTME a priori as only those voxels on subsequent scans with a T2 relaxation time ≥ 3 standard deviations (SD) above the baseline mean for that subject and muscle. Subject specific thresholds were required due to variation among both subjects and muscles. Knowing 8th/1e5/n19um4:0b6ePr M of abnormal voxels in a given muscle after BT inject for each MRI slice, a per muscle/per slice BTME volume (at .0015 voxel) could be calculated for each muscle and subject.

STUDY DESIGN

The primary objective of this series of experiments is to, in a research setting, better understand how spastic muscle and differing dilutions affect BT movement through muscle.

The secondary objective of this series of experiments is to, in a clinical setting, describe BT movement through a variety of lower extremity muscles with differing doses and dilutions of BT commonly used in clinical practice.

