Sample Size Justification The proposed sample sizes (6 patients for experiment #1, 15 patients for a within-group design in experiments #2-#4, or 25 patients for a between-groups design in experiments #2-#4) are primarily based on logistic considerations and conform to the exploratory (i.e., hypothesis-generating) nature of this pilot study. Because this is a pilot study, a formal sample size/power calculation is not required. Statistical Analyses For Experiment #1, descriptive analysis will be conducted to help inform the study design for the remaining experiments. The mean, standard deviation and morphology (either 3D reconstruction or number of MRI slices detecting a toxin effect) of BTME volume following injection in the LGM and MGM will be calculated for all 3 groups. If injections in the two muscles are similar (BTME volume +/- 20%) and there is no evidence of toxin movement outside of the injected muscle, then a within subject design will be implemented as described above. If not, we will use a between-subject design. Given the resources required for this study and the time commitment of the subjects, we propose a preliminary analysis for Experiments #2 and #3 after completion of MRI2 in 12 subjects if using a between subjects design (8 in each in standardized and 4 in the experimental injection groups using a 3:2 ratio) or 12 subjects if using the within-subjects design (12 comparison). For experiment #2 with a within-subjects design, we will examine the difference in BTME volume from baseline to 2 months following injection between the muscle sites injected with standard and experimental BT dilution in each patient using a paired t-test or Wilcoxon signed-rank test, as appropriate. For a between-subjects design, experiment #2 will be analyzed using a two-sample t-test or Wilcoxon rank sum test, as appropriate, to compare the mean 2-month difference in BTME volume in patients who received a standard dilution injection vs. those who received an experimental dilutio8n/15i/n1j9e4c:t0io6nPM in the spastic LGM. For either a within- or between-subjects design in experiment #3, we will use the paired t-test or Wilcoxon signed-rank test, as appropriate, to examine the difference in BTME volume from baseline to 2 months following injection between the spastic and non-spastic muscle sites injected in each patient. Experiment #4 will be analyzed descriptively, showing mean, standard deviation, median, and range of 2-month change in BTME volume for each combination of clinically injected site, dose, and dilution. This information will be used to generate hypotheses for future studies. Observational Group: N=6 observational subject MRI data will be analyzed the same as data from Experiment #4. All p-values will be two-sided with statistical significance evaluated at the 0.05 alpha level. Ninety-five percent confidence intervals for means will be calculated to assess the precision of the obtained estimates. Lack of any observed statistically significant differences between groups will not constitute evidence of equivalence or non-inferiority between dilution or spasticity groups; rather, estimates in each group will serve as preliminary data for further investigation (i.e., hypothesis-generating). All analyses will be performed in SAS Version 9.4 (SAS Institute, Inc., Cary, NC). Note: The statistical analysis section was written in conjunction with [name], MS, in the Division of Biostatistics and Epidemiology, Department of Healthcare Policy & Research.

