
The research questions for the present study series are as followed:

1. How does the movement and morphology of BT muscle effect (BTME) differ between standardized, research injections into spastic and non-spastic LGM?

2. How does the movement and morphology of BTME differ between a standardized, research injection into spastic LGM versus an injection using the same dose in a 100% greater dilution?

3. Is there a predictable BTME within a given muscle following lower extremity BT clinical injections based on clinical need?

We have two hypotheses.

First, we predict that BT muscle effect (BTME) will be greater in normal muscle than in spastic muscle.

Second, we hypothesize that BTME will increase with increasing dilution.

The standard BT injection will be an injection of 25 units of onobotulinumtoxinA (Botox[®]) diluted in 0.25cc of saline.

The experimental BT injection will be an injection of 25 units of onobutilinumtoxinA (Botox[®]) diluted in 0.50cc of saline.

Four experiments will be conducted to explore the research questions. At baseline, subjects will receive research injections that are decided based on the research protocol. Given the very small dosage of the research BT injections, we do not anticipate seeing any symptomatic effects in subjects. At 3 months following research injections, subjects will receive clinical injections that are decided based on their clinical need and are anticipated to result in clinical benefit for subjects. For all experiments subjects will have an MRI at baseline (MRIB), at 2M following research injections (MRI2), and at 2M following clinical injections (MRI3). If, for enrolled subjects who have previously had botulinum toxin injections below the knee, evidence of present botulinum toxin effect is seen on MRI, the subject will be ineligible for the research injections, MRI2, and MRI3 and will instead be offered to receive the clinical injections and then be exited from the study.

Experiment #1:

After a baseline MRI, 6 subjects will be randomized into three groups (N=2 in each group): standard injection in LGM, experimental injection in LGM, or experimental injection in MGM. All 6 subjects will receive a standard injection to the non-spastic LGM. Subjects will undergo a second MRI 2 months after the research injections, which will be used to confirm the design of the subsequent experiments.

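### Does Experiment #4 need a named reference scan, and do the Experiment #1 final scans need a stated analysis?

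*Combined protocol and SAP*

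**What the plan says.** Under Statistical Analyses, Experiment #4 is purely descriptive. It gives mean, standard deviation, "median, and range of 2-month change in BTME volume for each combination of clinically injected site, dose, and dilution", and no starting scan is named. In the same section the within-subjects analysis of Experiment #2 and the analysis of Experiment #3 do name baseline as the start. The between-subjects analysis of Experiment #2 uses a shorter form: "to compare the mean 2-month difference in BTME volume in patients who received a standard dilution injection".

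The Study Design section schedules three scans for experimental subjects: MRIB before the research injection, MRI2 two months after it, and MRI3 two months after the clinical injection. No scan is scheduled at the clinical injection itself.

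BTME is defined once, in the account of the proof-of-concept series that opens the document: "We defined BTME a priori as only those voxels on subsequent scans with a T2 relaxation time" at least 3 "standard deviations (SD) above the baseline mean for that subject and muscle".

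Experiment #1 has six subjects in three groups of two: "standard injection in LGM, experimental injection in LGM, or experimental injection in MGM". They also receive clinical injections and a final MRI. The Experiment #4 description, however, covers the subjects of Experiments #2 and #3. Sample Size Justification likewise counts Experiment #1 apart from "15 patients for a within-group design in experiments #2-#4, or 25 patients for a between-groups design in experiments #2-#4".

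For the six subjects with clinical injections only, the plan says: "Observational Group: N=6 observational subject MRI data will be analyzed the same as data from Experiment #4".

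**The concern.** Experiment #4 is the only experiment in which two scans precede the injection under study, and it is also one where the words naming baseline are missing. MRIB and MRI2 are both possible starting points. The 2-month label does not decide between them, because neither scan lies 2 months before MRI3.

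The choice could matter. MRI2 is timed to show the effect of the research injection. If it served as the reference, that effect would be subtracted from the result in any muscle that had been research-injected. Every Experiment #2/#3 subject has a research injection in the spastic lateral gastrocnemius or, in the within-subject design, in both heads. Eligibility also requires an indication to inject the gastrocnemius clinically. Two analysts could then report different values for the same muscle in the output that serves Research Question 3 and the secondary objective.

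Separately, six subjects would have a final scan that no stated analysis uses.

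**Working it through.** **1. Timeline.** Inputs, all from Study Design: MRI2 at 2 months (± 1 week); clinical injection 5 weeks (± 1 week) after MRI2 and no sooner than 3 months after the research injection; MRI3 2 months after the clinical injection. No window is stated for MRI3, so none is applied. One month = 365.25/12/7 = 4.35 weeks.

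- MRI2: 2 × 4.35 = week 8.7 (7.7 to 9.7).
- Clinical injection: 8.7 + 5 = week 13.7.
- MRI3: 13.7 + 8.7 = week 22.4, and 22.4/4.35 = 5.15 months. This reproduces the plan's own figure of about 5 months.
- MRI2 to MRI3: 5 + 8.7 = 13.7 weeks, or 3.15 months (12.7 to 14.7 weeks with the window).
- MRIB to MRI3 with the 3-month floor: 13.0 + 8.7 = 21.7 weeks at the earliest and 24.4 weeks at the latest.

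Neither interval is 2 months. The label can only mean time since the injection being studied. The shorter Experiment #2 wording uses it in that sense too.

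**2. Which scan the document points to.**

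- Only MRIB is called baseline. MRI2 never is.
- The BTME definition compares every later scan with one baseline mean and SD for that subject and muscle. MRI3 is a later scan in that sense.
- Experiment #3 and the within-subjects Experiment #2 name baseline. The between-subjects Experiment #2 drops the word with no change of meaning, and the Experiment #4 phrase has the same form.

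**3. What the change from MRIB amounts to.** By the definition, BTME at baseline is zero. If the 3-SD rule were applied to MRIB itself, 1 − Φ(3) = 0.00135, or about 0.13% of voxels, would exceed it under the Gaussian model. The change from MRIB is therefore in practice the BTME volume at MRI3, and the missing word changes nothing for an analyst who applies the definition.

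**4. What the other reading would do.** Let V3 and R be the BTME volumes at MRI3 and MRI2, both on the MRIB threshold.

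- MRIB reference: V3.
- MRI2 reference: V3 − R.
- Difference: V3 − (V3 − R) = R. The MRI2 result is negative whenever R exceeds V3.

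This holds only while the MRIB threshold is kept. If the mean and SD were re-estimated from MRI2, the volume at MRI3 would change as well, and the difference could not be written down from the document. Neither R nor V3 is given, so no percentage follows. In muscles without a research injection, R should be close to zero unless toxin spread, and the two readings nearly coincide.

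**5. The Experiment #1 scans.** Adding the six subjects would raise the total from 15 to 21 (within-subject) or from 25 to 31 (between-subject). The 95% CI half-width in SD units is t(0.975, n−1)/√n:

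| n | half-width |
|---|---|
| 15 | 0.554 |
| 21 | 0.455 |
| 25 | 0.413 |
| 31 | 0.367 |

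That is about 18% or 11% narrower, but only for a row to which every subject contributes, with equal SD. Rows are split by site, dose and dilution, and muscles are chosen by clinical need, so such a row is implausible and the real gain would be smaller. Adding the subjects also mixes exposures. In Experiment #1, four of six spastic lateral heads and two of six medial heads are research-injected. In the within-subject design, for example, previously injected heads would be 15 + 4 = 19 of 21 lateral and 15 + 2 = 17 of 21 medial, where before they were all injected.

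**The case for a change.** The best argument for a change has three parts.

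First, the BTME definition sits in an account of an earlier series that had one injection session and one scan before it. It could not foresee a second injection after MRI2, and the plan expressly carries over only that study's localization method. This is true, but the document contains no other definition, and the outcome cannot be computed without one.

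Second, the observational group is to be analysed in the same way, and its reference is the last scan before the clinical injection, which by analogy is MRI2. The analogy is weak. That group's pre-injection scan is also its only baseline, taken in legs naive to toxin. MRIB is the scan with those properties in experimental subjects.

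Third, the remedy would be a sentence or two. That is so, and naming MRIB would do no harm. It would only record what the rest of the plan already implies.

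Two reservations remain. The statement that toxin effects last about 12 weeks comes from the risk text and not from imaging data. It supports, but does not prove, the view that little research effect is left at weeks 21.7 to 24.4. Comparability with the observational group would suffer under an MRI2 reference, but the plan states no comparison or pooling of the two sources.

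**Conclusion.** No change follows. The missing reference scan is a gap that an analyst fills sensibly: the naming of the scans, the single BTME definition and the parallel wording for Experiment #2 all lead to MRIB, and the result is sound. The alternative reading would matter mainly in research-injected gastrocnemius heads, by R if the MRIB threshold is kept and by an unknown amount otherwise.

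The unused Experiment #1 scans are an omission from a descriptive output. Experiment #1 exists to choose the later design, and limiting Experiment #4 to the Experiments #2/#3 subjects is a legitimate choice that leaves its summaries valid. The most that inclusion could give is an interval 18% or 11% narrower, in a row unlikely to occur, at the price of mixed exposure within rows.

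This conclusion assumes that the proof-of-concept definition of BTME carries over to the present study and that Experiment #4 stays descriptive and hypothesis-generating, as the plan says.

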If, for Experiment #1, we find on MRI2 a similar appearance and volume of BTME (BTME volume +/-20%) for both the LGM and MGM receiving the experimental injection and that the BTME is contained within each muscle, we will have the option of proceeding with the within- subject design where each subject serves as his or her own control, receiving either the research or experimental injection in the spastic LGM and the alternative injection in the spastic MGM. If the within-subject design is used, 15 subjects will be recruited. If the BTME volumes for the LGM and MGM receiving the experimental injection are not within +/- 20% of each other, or we see on the MRI that the BTME is not contained within each injected muscle, then we will use a between subject design where subjects will be randomized to receive either the experimental or standard injection to the spastic LGM and 25 subjects will be recruited.

Subjects will receive clinical injections 3 months following the research injections and undergo a final MRI 2 months following clinical injections. Recruitment for the subsequent experiments will begin after data analysis from the second MRI in experiment #1 is complete.

Experiment #2 (Effect of dilution, answer Research Question #1):

If using a within-subject design, subjects will be randomized to receive a standard injection to either the LGM or MGM. The experimental injection will be delivered to the muscle not receiving the standard injection. If using a between-subjects design, subjects will be randomized to receive either a standardized injection in the LGM or an experimental injection in the LGM. On the same day of, but before the injection, the MRIB will be acquired. Using the localization schema proposed in our proof-of-concept study, the baseline scan will be used to determine the coordinates and depth of the injection into a given muscle. Two months (+/- 1 week) after the injection, subject will report for MRI2 and will be considered finished with Experiment #2.

He/she will be scheduled for the "clinical" injection 5 weeks (+/- 1 week) from that time, which will be evaluated in Experiment #4.

Experiment #3 (spastic vs. non spastic muscle, answer Research Question #2):

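### If the within-subject option is used, Experiment #2's paired test estimates the dilution effect averaged over LGM and MGM, not the spastic-LGM effect that Research Question 2 refers to, and the plan should say so

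*Combined protocol and SAP*

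**What the plan says.** **The question.** In Study Design, Research Question 2 compares "a standardized, research injection into spastic LGM versus an injection using the same dose in a 100% greater dilution". The matching hypothesis is "Second, we hypothesize that BTME will increase with increasing dilution", which names no muscle. Experiment #2 carries the label of Research Question 1 and Experiment #3 that of Research Question 2. By content they are the other way round, and Experiment #2 is the dilution experiment.

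**The two design options.** The between-subjects option (25 patients) randomizes patients to one dilution or the other, both in the spastic LGM. For the within-subject option (15 patients), Experiment #2 says: "If using a within-subject design, subjects will be randomized to receive a standard injection to either the LGM or MGM". The experimental injection goes into the other head. No allocation ratio is given.

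**The analysis.** For the within-subject option, Statistical Analyses uses a paired t-test or signed-rank test on the difference "between the muscle sites injected with standard and experimental BT dilution in each patient". It names no term for muscle.

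**The gate.** In Experiment #1, "6 subjects will be randomized into three groups (N=2 in each group"), and the groups are "standard injection in LGM, experimental injection in LGM, or experimental injection in MGM". Also, "All 6 subjects will receive a standard injection to the non-spastic LGM". The within-subject option becomes available if LGM and MGM look similar, agree in volume to within 20% after the experimental injection, and the effect stays inside each muscle.

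**The concern.** Under the within-subject option no patient has both dilutions in a spastic LGM. Each pair crosses heads, and in roughly half the patients the standard comparator lies in the MGM. The two design options therefore estimate different quantities for one research question, and Experiment #1 data decide which is used.

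The estimates are meant as preliminary data for later work. A later study that took the paired result as an LGM effect would start from the wrong quantity if the heads respond differently to dilution, and nothing in the planned output would reveal that.

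**Working it through.** The plan gives no BTME values, SD or correlation, so there is no figure of its own to reproduce. The main result is algebraic; every BTME value, SD and correlation below is an assumption.

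**1. What the paired mean estimates.** Let S_L, E_L, S_M, E_M be mean BTME for the standard (S) and experimental (E) dilution in LGM (L) and MGM (M). A patient contributes either E_L − S_M or E_M − S_L. With equal allocation:

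[(E_L − S_M) + (E_M − S_L)]/2 = [(E_L − S_L) + (E_M − S_M)]/2

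This is the average of the two head-specific dilution effects. The signed-rank alternative uses the same cross-head pairs, so it does not restore an LGM contrast.

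**2. A constant head difference.** If LGM exceeds MGM by m at both dilutions, m cancels under equal allocation. Fifteen patients cannot split equally. At 8/7 the remainder is (8m − 7m)/15 = m/15.

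**3. Departure from the LGM effect.** Average minus LGM effect = ½[(E_M − S_M) − (E_L − S_L)]. This is zero only if the heads respond equally to dilution.

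**4. What Experiment #1 can show.** On the spastic side it observes S_L, E_L and E_M. It never observes S_M, so E_M − S_M cannot be formed. The non-spastic injection is also in the LGM. Even a perfect match at the experimental dilution settles nothing: with S_L = 1.0 and E_L = E_M = 1.5 the LGM effect is 0.50, but the average is 0.60 if S_M = 0.8 and 0.375 if S_M = 1.25.

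The gate is also imprecise. In simulation with two patients per muscle and lognormal volumes, a ratio of means between 0.8 and 1.2 occurred as follows:

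| CV | Heads truly equal | MGM truly 50% larger |
|---|---|---|
| 0.3 | 51% | 21% |
| 0.5 | 33% | 23% |

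**5. Illustration at the gate's edge.** Take E_L = 100, E_M = 80 and S_L = s.

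| s | LGM effect | Average if S_M = s | Error | Average if S_M = 0.8s | Error |
|---|---|---|---|---|---|
| 50 | 50 | 40 | −20% | 45 | −10% |
| 70 | 30 | 20 | −33% | 27 | −10% |
| 80 | 20 | 10 | −50% | 18 | −10% |

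In the last column the average is 0.9(100 − s), hence 10% throughout. If the tolerance must hold whichever head is the reference, E_M is at least 100/1.2 = 83.3, and with S_M = s the error is 8.3 points instead of 10.

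**6. Precision, in units of a common SD, for a 7/8 split.**
- Paired average: √(2(1 − r)/15) = 0.31, 0.26, 0.20 at r = 0.3, 0.5, 0.7.
- One head, between patients: √(1/7 + 1/8) = 0.52 at any r.
- Difference between the two head effects: √(2(1 + r)(1/7 + 1/8)) = 0.83, 0.90, 0.95 at the same r.

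**The case against.** A reader might infer that the plan will present the paired result as an LGM effect. The documents do not say so. Statistical Analyses describes the within-subject test by injected sites and names the spastic LGM only for the between-subjects test. The dilution hypothesis and the primary objective speak of muscle in general, and Research Question 2 names the LGM for the standard injection without naming a muscle for the greater dilution. A two-head average answers the hypothesis. The mismatch is with the wording of one research question.

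A reader might also take 20% to 50% as the expected bias. It is an edge case: the MGM sits at the limit of the tolerance and the heads do not differ at all at the standard dilution. If they differ proportionally the error is 10%, and the documents do not say which applies.

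It is tempting, too, to let the LGM-only contrast replace the paired estimate. With a 10-point bias and an assumed SD of 30 points (r = 0.5), root mean squared error for the LGM effect is √(10² + (0.258 × 30)²) = 12.6 for the paired estimate against 0.518 × 30 = 15.5 for LGM-only. The paired estimate is the closer one unless the SD is below about 22, since 10/√(0.268 − 0.067) = 22.

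Finally, the option is conditional, the switch between heads is openly described, and the study is a hypothesis-generating pilot. All of this stands and lowers the weight of the point. It does not change what the paired test estimates, and the gate does not test the assumption of equal response to dilution.

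**Conclusion.** The point holds as a minor one. If the within-subject option is taken, the paired test estimates the dilution effect averaged over the two spastic gastrocnemius heads. Under equal allocation this is an identity and needs no assumed value; with 8/7, a further 1/15 of any constant head difference remains. Reading the result as the spastic-LGM effect requires equal response to dilution in both heads, which Experiment #1 cannot establish because no group receives the standard injection in the spastic MGM.

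The size of any departure is unknown. The 10% to 50% range rests wholly on assumed volumes. The documents do not support calling the paired test biased for the dilution hypothesis, or saying that an LGM claim is planned from it.

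**What to change.** If the within-subject option is used:

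1. Keep the paired analysis as the main estimate. Add a term for which muscle received the standard injection, so that the two allocation groups count equally. Define and report the result as the dilution effect averaged over the two spastic gastrocnemius heads. The term costs almost no precision (½ × √(1/7 + 1/8) = 0.26 SD at r = 0.5, as before). It also protects power: in simulation with an 8/7 split and an effect of 0.8 SD of the paired differences, a head difference of 1 SD cut the power of the unadjusted paired test from about 82% to 62%, while the adjusted analysis stayed at about 82%.
2. Beside it, report descriptively with 95% CIs the randomized LGM-only contrast (about 7 v 8 patients), the same contrast for the MGM, and their difference. Make no LGM-specific claim from the paired result alone.

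The cost is some SAP wording and one table from data already collected. The downside is width: SE about 0.52 SD for each head and 0.90 SD for the difference (r = 0.5 assumed), against 0.26 SD for the paired average. The table supports the paired estimate; it cannot rule out a difference between heads, and the report should say so.
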